4.2. Schedule of Activities

Table 1: Study Activities for Study 109MS310 - Table 1 of 2

Tests and Assessments	Screening	Treatment Period												Final Follow-Up Visit ¹
		Baseline	Week 4 (Day 28 ±3 days)	Week 8 (Day 56 ±3 days)	Week 12 (Day 84 ±3 days)	Week 24 (Day 168 ±5 days)	Week 36 (Day 252 ±5 days)	Week 48 (Day 336 ±5 days)	Week 60 (Day 420 ±5 days)	Week 72 (Day 504 ±5 days)	Week 84 (Day 588 ±5 days)	Week 96 (Day 672 ±5 days)	4 weeks ±5 days after final dose	
Informed Consent ²	X													
Medical History ³	X													
Hepatitis B and C Screen	X													
HIV Testing (As Per Local Guidelines) ⁴	X													
MRI Scan ⁵	X													
Physical Examination ⁶	X							X				X		
Vital Signs ⁷	X	X	X	X	X	X	X	X		X		X		X
12-Lead ECG		X						X				X		
Hematology (CBC With Differential) ⁸	X	X	X	X	X	X	X	X	X	X	X	X		X
Blood Chemistry	X	X	X	X		X		X				X		X

CONFIDENTIAL

The information contained herein may not be used, disclosed, or published without the written consent of Biogen MA Inc.

Tests and Assessments	Screening	Treatment Period												Final Follow-Up Visit ¹
		Baseline (Day 1)	Week 4 (Day 28 ±3 days)	Week 8 (Day 56 ±3 days)	Week 12 (Day 84 ±3 days)	Week 24 (Day 168 ±5 days)	Week 36 (Day 252 ±5 days)	Week 48 (Day 336 ±5 days)	Week 60 (Day 420 ±5 days)	Week 72 (Day 504 ±5 days)	Week 84 (Day 588 ±5 days)	Week 96 (Day 672 ±5 days)		
Lymphocyte Subset Analysis ⁸	X	X	X	X	X	X	X	X		X		X	X	
Serum Pregnancy Test ⁹	X													
Urine Pregnancy Test ^{9, 10}		X			X	X	X	X	X	X	X	X		
Dispense BG00012		X			X	X	X	X	X	X	X	X		
BG00012 Administration								X						
Concomitant Therapy and Procedures									X					
AE Recording								X						
SAE Recording														

CONFIDENTIAL

The information contained herein may not be used, disclosed, or published without the written consent of Biogen MA Inc.

Phase 3b Study on the Effect of BG00012 on Lymphocyte Subsets and Immunoglobulins in Subjects With RRMS

AE = adverse event; CBC = complete blood count; DNA = deoxyribonucleic acid; ECG = electrocardiogram; [REDACTED]; HIV = human immunodeficiency virus; Ig = immunoglobulin; LLN = lower limit of normal; MRI = magnetic resonance imaging; MS = multiple sclerosis; [REDACTED]; SAE = serious adverse event.

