¹ Subjects will have a final Follow-Up Visit 4 weeks after taking their final dose, regardless of whether they complete the treatment period or discontinue prematurely, unless they have a lymphocyte count <LLN. Subjects who have a lymphocyte count <LLN will continue protocol-required visits and assessments per Section 11.3.

² Written informed consent must be obtained prior to performing any study-related procedures.

³ Medical history will include gastrointestinal abnormalities within the previous 6 months, as well as duration of MS (time since diagnosis), relapse history, and treatments for MS.

⁴ HIV testing will be done locally at Screening only if required, per local guidelines.

⁵ If required per local guidelines and if not already available within the previous 3 months, an MRI scan should be performed locally before starting therapy with BG00012.

⁶ Physical examination includes height and weight measurements, as well as a neurological examination.

⁷ Vital signs will include diastolic and systolic blood pressure, heart rate, and temperature. Subjects must be seated for 5 minutes prior to having their pulse and blood pressure measured.

⁸ Whole blood may also be collected for lymphocyte functional tests. Lymphocyte subset analysis will include total Ig and IgG subclasses, and may also include assays for [REDACTED] and VLA-4 expression. In subjects with a confirmed lymphocyte count <500/mm³ lymphocyte testing must be performed every 4 weeks; if the lymphocyte count remains <500/mm³ for 24 weeks, study treatment will be temporarily withheld for 24 weeks or until the lymphocyte count recovers to LLN, whichever is sooner, and testing continues to be every 4 weeks; if the lymphocyte count does not recover to LLN within 24 weeks while study treatment is temporarily withheld, study treatment will be withheld permanently, and testing will be performed every 12 weeks for an additional 24 weeks or until the lymphocyte count recovers to LLN, or until the end of the study, whichever is sooner.

⁹ Females of childbearing potential only. Results must be known to be negative prior to dispensing BG00012.

¹⁰ Pregnancy test may be repeated locally at additional timepoints if needed, per local guidelines.

¹¹ Sample can be collected at any point during the study in subjects who have signed a separate informed consent form.

CONFIDENTIAL

The information contained herein may not be used, disclosed, or published without the written consent of Biogen MA Inc.

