Table 2: Study Activities for Study 109MS310 - Table 2 of 2

Tests and Assessments	[REDACTED]	Discontinuation and/or Withdrawal Visit ²	Lymphocyte Follow-Up Visit ³	Unscheduled Visit for Abnormal Laboratory Results (Other Than Lymphocytes)
		These visits can be combined. If these visits are not combined, any assessment that was performed within the past 2 weeks (or the interval noted in the footnotes) does not need to be repeated unless clinically indicated.		
Physical Examination ⁴	X		X	
Vital Signs ⁵	X	X	X	
Hematology (CBC With Differential)	X	X	X	X ⁶
Blood Chemistry	X	X		X ⁷
[REDACTED]				
Lymphocyte Subset Analysis		X	X	
[REDACTED]				
Concomitant Therapy and Procedures		X		
AE Recording		X		
SAE Recording	Monitor and record throughout the study.			

AE = adverse event; ALT = alanine transaminase; AST = aspartate transaminase; CBC = complete blood count; [REDACTED]; LLN = lower limit of normal; [REDACTED]; SAE = serious adverse event; ULN = upper limit of normal; WBC = white blood cell.

² Discontinuation refers to discontinuation of study treatment. Withdrawal refers to withdrawal of subjects from study. The Discontinuation and/or Withdrawal Visit should be conducted as soon as possible and no later than 2 weeks after their last dose of study treatment.

CONFIDENTIAL

The information contained herein may not be used, disclosed, or published without the written consent of Biogen MA Inc.

³ Subjects who complete, temporarily withhold, or permanently discontinue study treatment for any reason and have a lymphocyte count <LLN will continue protocol-required visits and assessments and will also be followed up every 4 weeks for 24 weeks, then every 12 weeks (**unless clinically indicated more often or at the Investigator's discretion**) until the lymphocyte count is \geq LLN or for up to 48 weeks following drug discontinuation, whichever occurs sooner.

⁴ Physical examination includes height and weight measurements, as well as a neurological examination.

⁵ Vital signs will include diastolic and systolic blood pressure, heart rate, and temperature. Subjects must be seated for 5 minutes prior to having their pulse and blood pressure measured.

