7.2.3. Follow-Up

[figure not shown]
Subjects are to return to the study site for a Follow-Up Visit 4 weeks after their last dose of study treatment. The final study visit will be Week 100.

Subjects who temporarily withhold or permanently discontinue BG00012 for any reason and have a lymphocyte count <LLN will be followed every 4 weeks for 24 weeks, then every 12 weeks (**unless clinically indicated more often or at the Investigator's discretion**) until the lymphocyte count is \geq LLN or for up to 48 weeks following drug discontinuation, whichever occurs sooner; see [Section 11.3](#)). Subjects whose lymphocyte count remains <LLN at the end of the study (Week 96) will complete the final Follow-Up Visit and will then be followed up outside of this protocol at the Investigator's discretion.

CONFIDENTIAL

The information contained herein may not be used, disclosed, or published without the written consent of
Biogen MA Inc.

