10. DISCONTINUATION OF STUDY TREATMENT AND/OR WITHDRAWAL OF SUBJECTS FROM THE STUDY

10.1. Discontinuation of Study Treatment

A subject *must* permanently discontinue study treatment for any of the following reasons:

- The subject becomes pregnant. Study treatment must be discontinued immediately. Report the pregnancy according to the instructions in Section 15.4.1.
- The subject withdraws consent to continue study treatment.
- The subject experiences a medical emergency that necessitates permanent discontinuation of study treatment.
- The subject is unable to tolerate study treatment at 240 mg BID (see Section 11.2.4).
- The subject receives any concomitant medications not allowed by the protocol.
- The subject experiences any of the laboratory abnormalities requiring permanent discontinuation of treatment defined in [Table 3](#).
- The subject experiences more than 1 deviation of the same laboratory parameter that meets the threshold limits defined in [Table 3](#) at any time during the study.
- The subject experiences more than 2 different deviations of laboratory parameters that meet the threshold limits defined in [Table 3](#) at any time during the study. On a third occasion, the subject is required to discontinue dosing for the remainder of the study.
- If a subject has a lymphocyte count $<500/\text{mm}^3$ persisting for more than 24 weeks consecutively, study treatment must be temporarily withheld. Study treatment may be resumed after lymphocyte counts recover $>\text{LLN}$ on 2 consecutive occasions at least 4 weeks apart. If the subject develops a lymphocyte count $<500/\text{mm}^3$ on 1 occasion (confirmed by repeat testing) on resumption of study treatment, the subject must permanently discontinue study treatment and will continue protocol-required visits and assessments (see Section 11.3).
- If a subject's lymphocyte count remains $<\text{LLN}$ for 24 weeks consecutively after study treatment has been temporarily withheld due to lymphocyte count $<500/\text{mm}^3$ for more than 24 weeks, the subject must permanently discontinue study treatment.
- At the discretion of the Investigator for medical reasons or for noncompliance.

The reason for discontinuation of study treatment must be recorded in the subject's case report form (CRF).

Subjects who discontinue treatment may remain in the study and continue protocol-required tests and assessments.

CONFIDENTIAL

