15.3. Monitoring and Recording Events

15.3.1. Adverse Events

Any AE experienced by the subject between the time of first dose of study treatment and the final Follow-Up Visit is to be recorded on the CRF, regardless of the severity of the event or its relationship to study treatment.

CONFIDENTIAL

The information contained herein may not be used, disclosed, or published without the written consent of Biogen MA Inc.

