15.3.2. Serious Adverse Events

Any SAE experienced by the subject between the time of the signing of the ICF and the final Follow-Up Visit is to be recorded on an SAE form, regardless of the severity of the event or its relationship to study treatment. SAEs must be reported to Biogen or designee within 24 hours as described in Section 15.3.3. Follow-up information regarding an SAE also must be reported with 24 hours.

Subjects will be followed for all SAEs until the final Follow-Up Visit. Thereafter, the event should be reported to Biogen or designee only if the Investigator considers the SAE to be related to study treatment.

Any SAE that is ongoing when the subject completes or discontinues the study will be followed by the Investigator until the event has resolved, stabilized, or returned to baseline status.

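### For subjects who stop BG00012 early with a normal lymphocyte count and stay in the study, the AE window closes 4 weeks after the last dose while visits continue to Week 96, and the SAE rules conflict

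*Protocol*

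**What the plan says.** - **AE window.** Protocol Section 15.3.1: "Any AE experienced by the subject between the time of first dose of study treatment and the final Follow-Up Visit is to be recorded".
- **SAE window.** Section 15.3.2 starts at consent and states: "Subjects will be followed for all SAEs until the final Follow-Up Visit". It then adds: "Thereafter, the event should be reported to Biogen or designee only if the Investigator considers the SAE to be related to study treatment". Section 15.3.3 repeats both rules.
- **Date of that visit.** The Table 1 column is timed at "4 weeks ±5 days after final dose". Footnote 1 reads: "Subjects will have a final Follow-Up Visit 4 weeks after taking their final dose, regardless of whether they complete the treatment period or discontinue prematurely". Its one exception is for subjects with a count below LLN, who go on with visits under Section 11.3.
- **Staying in the study.** Section 10.1: "Subjects who discontinue treatment may remain in the study and continue protocol-required tests and assessments". Section 7.1 also allows other MS therapies after permanent discontinuation, once the Medical Monitor has been consulted.
- **Other uses of the term.** Section 7.2.3 puts the Follow-Up Visit 4 weeks after the last dose and then says: "The final study visit will be Week 100". Sections 11.3.1 and 11.3.3 use the final Follow-Up Visit as the point where continued testing stops. Section 11.3.3 does so for subjects whose count has been below LLN for 48 weeks.
- **Schedule.** The SAE row of Table 2 says: "Monitor and record throughout the study".
- **SAP.** Section 5.4.1 counts an event as treatment-emergent if it starts on or after the first dose, and sets no end date. Section 5.4.6 lists AEs from the lymphocyte follow-up period. Under Section 5.3.3, that follow-up analysis generally covers subjects with at least one count below LLN on treatment.

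**The concern.** The safety window hangs on a visit whose name carries two dates. For a subject who completes treatment the dates coincide at Week 100. For a subject who stops early and stays, they can be more than a year apart.

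On the literal reading, such a subject keeps attending, gives blood and may be on a new MS drug, but the site has no stated duty to record AEs. Under Section 15.3.2, later SAEs are reported only if the investigator judges them related to BG00012. Sites that read the term as the end of study would record everything, so safety capture would differ by site and by lymphocyte status at stopping. Delayed infections are the kind of event that could be lost or filtered in this way. Section 5.3.2 itself reports PML in the setting of prolonged lymphopenia.

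There is an opposite problem in the analysis. Where late events are recorded, the SAP definition counts them as treatment-emergent however long ago BG00012 was stopped.

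**Working it through.** **1. The plan's own timeline.** Section 7.2 gives screening within 4 weeks of Baseline, 96 weeks of treatment and a final visit, which Table 1 puts 4 weeks after the last dose.

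- Participation: 4 + 96 + 4 = 104 weeks, as stated.
- Last visit for a completer: 96 + 4 = Week 100, as stated.

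**2. Length of the uncovered period.** Let L be the week of the last dose. The window closes at week L + 4, and scheduled treatment-period visits run to Week 96.

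Gap to Week 96 = 96 − (L + 4) = 92 − L weeks.

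| Last dose (week) | Window closes (week) | Gap to Week 96 (weeks) |
|---|---|---|
| 0 | 4 | 92 |
| 12 | 16 | 80 |
| 24 | 28 | 68 |
| 48 | 52 | 44 |
| 72 | 76 | 20 |
| 92 | 96 | 0 |

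If the stay is counted to Week 100, each gap is 4 weeks longer (96 − L). The ceiling is therefore about 92 weeks to Week 96.

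**3. One term, two dates.** For an early stopper at or above LLN, footnote 1 fixes the visit at L + 4. In Section 11.3.3 testing continues after 48 weeks below LLN and stops at the same-named visit. A visit 4 weeks after the last dose cannot end testing that is still running 48 weeks after it, so there the term must mean the end of study. Section 7.2.3 gives both dates in adjacent sentences.

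**4. Who falls in the gap.**

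- Count below LLN at stopping: exempt from the 4-week visit by footnote 1. No replacement date is given, so their AE end point is undefined once the count recovers.
- Unable to tolerate 240 mg BID: withdrawn after the 4-week visit (Sections 10.2 and 11.2.4), so no gap.
- Withdrawn from the study for any other reason: no later visits, so no gap.
- Left: subjects who stop for another Section 10.1 reason (for example a Table 3 laboratory criterion, a disallowed medication or investigator decision) with a count at or above LLN, and who stay.

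**5. How many.** Section 16.7 allows 10% discontinuation: 200 × 0.90 = 180 evaluable at Week 48. It does not say how many of the other 20 would stay, when they would stop, or what their counts would be. No subject number or subject-time follows from this.

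**The case against.** The best defence is that the protocol, read as a whole, already requires recording to the last visit. Section 14.1 lists AE and SAE recording among the safety assessments, and Section 10.1 says those who stay may continue the required assessments. Section 15.6.1 tells investigators to record all AEs and gives no cut-off. The SAP plans to list AEs from lymphocyte follow-up, which can run 48 weeks past discontinuation. In the text available here, the columns spanned by the AE row of Table 1 cannot be read.

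This shows that the intention was probably broader than the literal window. It does not settle the point, because a general duty does not override a section that states explicit start and end points. No passage extends AE recording to the last visit for stayers at or above LLN. The SAP listing mainly serves subjects who had a low count on treatment.

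Two limits stand in full. A reader might infer that every early stopper loses AE recording. The documents do not support that, since footnote 1 exempts counts below LLN and intolerant subjects leave the study. A reader might also infer that SAE recording simply stops. It does not: the schedule says otherwise, and related SAEs stay reportable after the visit. For SAEs the fault is two conflicting rules, one of which applies a causality filter.

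An open-ended treatment-emergent definition is also explicit and agrees with Protocol Section 16.4.2.1. A separate table for late events is therefore an improvement to the analysis, not the correction of an error.

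**Conclusion.** The point holds for a defined group: subjects who stop BG00012 early with a count at or above LLN, are not withdrawn for intolerance, and remain in the study. For them the written AE window, and unconditional SAE reporting, end at week L + 4. That leaves 92 − L weeks to Week 96: 68 weeks for a Week 24 stop and at most about 92. This assumes that the subject stays to Week 96 and that the site follows Section 15.3 together with footnote 1 literally.

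Two larger-sounding statements should be avoided. A reader might take about 72 weeks as the upper limit. That is the figure for a Week 24 stop counted to Week 100, or a Week 20 stop counted to Week 96, and it is not a maximum. A reader might also multiply the 20 subjects in the 10% allowance by such a gap to get lost subject-years. The allowance describes subjects not evaluable at Week 48 and says nothing about who stays or when they stop, so the total cannot be computed.

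The primary endpoint is not touched. The defect concerns completeness and consistency of safety capture, and it should be corrected.

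**What to change.** 1. In Protocol Sections 15.3.1 to 15.3.3, end AE and SAE recording at the subject's last study visit, defined as the 4-week Follow-Up Visit or any later protocol visit, whichever is last.
2. Reconcile the visit's name and date wherever it appears: Table 1 with footnote 1, Table 2, Sections 7.2.3, 11.3.1 and 11.3.3, the synopsis, and the matching text in SAP Section 2. Changing Table 1 alone would leave the ambiguity in place. The text should also give an end point for subjects below LLN whose count later recovers.
3. In SAP Section 5.4.1, keep the treatment-emergent definition and add a separate table of events with onset more than 28 days after the last dose. The 28-day cut matches the 4-week visit and is a proposed convention; it is not taken from the documents.

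**Cost.** No new visits or samples: AE questions at visits already scheduled, and one extra table. Items 1 and 2 need a protocol amendment submitted to ethics committees under Section 19.3, possibly with a consent form change. The SAP describes subjects as already treated, so the change may come mid-study and would not recover events that went unrecorded before it took effect.

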15.3.2. Serious Adverse Events

Any SAE experienced by the subject between the time of the signing of the ICF and the final Follow-Up Visit is to be recorded on an SAE form, regardless of the severity of the event or its relationship to study treatment. SAEs must be reported to Biogen or designee within 24 hours as described in Section 15.3.3. Follow-up information regarding an SAE also must be reported with 24 hours.

Subjects will be followed for all SAEs until the final Follow-Up Visit. Thereafter, the event should be reported to Biogen or designee only if the Investigator considers the SAE to be related to study treatment.

Any SAE that is ongoing when the subject completes or discontinues the study will be followed by the Investigator until the event has resolved, stabilized, or returned to baseline status.

15.3.3. Immediate Reporting of Serious Adverse Events

In order to adhere to all applicable laws and regulations for reporting an SAE, the study site must formally notify Biogen or designee within 24 hours of the study site staff becoming aware of the SAE. It is the Investigator's responsibility to ensure that the SAE reporting information and procedures are used and followed appropriately.

Reporting Information for SAEs

Any SAE that occurs between the time that the subject has signed the ICF and the final Follow-Up Visit must be reported to Biogen or designee within 24 hours of the study site staff becoming aware of the event. Thereafter, the event should be reported only if the Investigator considers it related to study treatment.

A report **must be submitted** to Biogen or designee regardless of the following:

- Whether or not the subject has undergone study-related procedures
- Whether or not the subject has received study treatment
- The severity of the event
- The relationship of the event to study treatment

To report initial or follow-up information on an SAE, fax a completed SAE form; refer to the Study Reference Guide for complete contact information.

15.3.3.1. Deaths

Death is an outcome of an event. The event that resulted in death should be recorded on the appropriate CRF. All causes of death must be reported as SAEs within 24 hours of the site becoming aware of the event. The Investigator should make every effort to obtain and send

CONFIDENTIAL

The information contained herein may not be used, disclosed, or published without the written consent of Biogen MA Inc.

death certificates and autopsy reports to Biogen or designee. The term death should be reported as an SAE only if the cause of death is not known and cannot be determined.

15.3.4. Suspected Unexpected Serious Adverse Reactions

Suspected unexpected serious adverse reactions (SUSARs) are SAEs that are unexpected and judged by the Investigator or Biogen to be related to the study treatment administered.

Biogen or designee will report SUSARs to the appropriate regulatory authorities and Investigators as required, according to local law.

15.4. Procedures for Handling Special Situations

15.4.1. Pregnancy

Subjects should not become pregnant or impregnate their partners during the study and for 30 days after their last dose of study treatment. If a female subject becomes pregnant, study treatment must be discontinued *immediately*.

The Investigator must report a pregnancy by faxing the appropriate form to Biogen or designee within 24 hours of the study site staff becoming aware of the pregnancy at the fax number provided in the Study Reference Guide. The Investigator or study site staff must report the outcome of the pregnancy to Biogen or designee.

Congenital abnormalities and birth defects in the offspring of male or female subjects should be reported as an SAE if conception occurred during the study treatment period.

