15.1.2. Serious Adverse Event

An SAE is any untoward medical occurrence that at any dose:

- Results in death
- In the view of the Investigator, places the subject at immediate risk of death (a life-threatening event); however, this does not include an event that, had it occurred in a more severe form, might have caused death
- Requires inpatient hospitalization or prolongation of existing hospitalization
- Results in persistent or significant disability/incapacity
- Results in a congenital anomaly/birth defect

An SAE may also be any other medically important event that, in the opinion of the Investigator, may jeopardize the subject or may require intervention to prevent one of the other outcomes

CONFIDENTIAL

The information contained herein may not be used, disclosed, or published without the written consent of Biogen MA Inc.

listed in the definition above. (Examples of such medical events include allergic bronchospasm requiring intensive treatment in an emergency room or convulsions occurring at home that do not require an inpatient hospitalization.)

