15.5. Contraception Requirements

Subjects of childbearing potential must practice effective contraception (as determined by the Investigator) during the study and be willing and able to continue contraception for 30 days after their last dose of study treatment. In addition, male subjects should not donate sperm for the duration of the study and for at least 30 days after their last dose of study treatment.

For the purposes of this study, women who do not meet one of the following criteria listed below are considered to be physiologically capable of becoming pregnant and are, therefore, defined as women of childbearing potential:

- Postmenopausal
 - 12 months of natural (spontaneous) amenorrhea without an alternative medical cause and a serum follicle-stimulating hormone level >40 mIU/mL
 - 6 weeks after surgical bilateral oophorectomy with or without hysterectomy
- Posthysterectomy
- Female surgical sterilization (e.g., bilateral tubal ligation)

For the purposes of the study, highly effective contraception is defined as use of 1 or more of the following:

For females:

- Established use of oral, injected, or implanted hormonal methods of contraception.
- Placement of an intrauterine device or intrauterine system.
- Barrier methods of contraception with use of a spermicide: condom or occlusive cap (diaphragm or cervical/vault caps) with spermicidal foam/gel/film/cream suppository. The use of barrier contraceptives should always be supplemented with the use of a spermicide.
- Male surgical sterilization (with the appropriate postvasectomy documentation of the absence of sperm in the ejaculate). (For female subjects participating in the study, male sexual partners must have undergone surgical sterilization.)

For males:

- Effective male contraception includes a vasectomy with negative semen analysis at follow-up, or the use of condoms with spermicide.

True abstinence, when this is consistent with the preferred and usual lifestyle of the subject, can be considered an acceptable method of contraception based on the evaluation of the Investigator who should also take into consideration the duration of the clinical trial. Periodic abstinence (e.g., calendar, ovulation, symptothermal, postovulation methods) and withdrawal are not considered acceptable methods of contraception.

Pregnancy reporting is described in Section 15.4.1.

CONFIDENTIAL

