15.6. Safety Responsibilities

15.6.1. The Investigator

The Investigator's responsibilities include the following:

- Monitor and record all AEs, including SAEs, regardless of the severity or relationship to study treatment.
- Determine the seriousness, relationship, and severity of each event.
- Determine the onset and resolution dates of each event.
- Monitor and record all pregnancies and follow up on the outcome of the pregnancy.
- Complete an SAE form for each SAE and fax it to Biogen or designee within 24 hours of the study site staff becoming aware of the event.
- Pursue SAE follow-up information actively and persistently. Follow-up information must be reported to Biogen or designee within 24 hours of the study site staff becoming aware of new information.
- Ensure all AE and SAE reports are supported by documentation in the subjects' medical records.
- Pursue AE follow-up information, if possible, until the event has resolved or has become stable.
- Report SAEs to local ethics committees, as required by local law.

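### The SAE rule for birth defects ends with the study treatment period, but the protocol's own contraception window runs to 30 days after the last dose

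*Protocol*

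**What the plan says.** Protocol 15.4.1 opens with the avoidance period: "Subjects should not become pregnant or impregnate their partners during the study and for 30 days after their last dose of study treatment". Section 15.5 requires subjects of childbearing potential to "be willing and able to continue contraception for 30 days after their last dose of study treatment", and inclusion criterion 3 in Section 8.1 repeats this. Section 15.5 also bars sperm donation for at least the same 30 days.

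The last sentence of 15.4.1 uses a different limit. Birth defects in the offspring of male or female subjects "should be reported as an SAE if conception occurred during the study treatment period". The section does not define *study treatment period*. Sections 7.1 and 7.2 use Treatment Period for the planned 96 weeks, but in 15.4.1 the phrase could equally mean the time a subject is actually dosed.

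Other provisions also bear on these events:

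- Section 15.1.2 lists among the SAE criteria an event that "Results in a congenital anomaly/birth defect", with no limit on the conception date.
- Section 15.3.3 says "Any SAE that occurs between the time that the subject has signed the ICF and the final Follow-Up Visit must be reported to Biogen" or its designee, within 24 hours of the site becoming aware. After that visit: "Thereafter, the event should be reported only if the Investigator considers it related to study treatment". Section 15.3.2 says the same.
- Section 15.4.1 requires a pregnancy to be reported within 24 hours and adds: "The Investigator or study site staff must report the outcome of the pregnancy to Biogen or designee".
- Section 15.6.1 gives the Investigator this duty: "Monitor and record all pregnancies and follow up on the outcome of the pregnancy".
- Table 1 puts the final Follow-Up Visit 4 weeks ±5 days after the final dose. Its first footnote applies this to completers and early stoppers alike, unless the lymphocyte count is below LLN.

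**The concern.** The protocol requires contraception for 30 days after dosing, yet its birth-defect rule stops earlier and gives no reason. A conception inside the protocol's own window can therefore lead to a birth defect that the specific SAE rule does not reach. By the time of birth, the general SAE rule has usually become conditional on the Investigator's view of causality.

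What is at stake is how such an event arrives. As an SAE, it comes within 24 hours and can enter the SUSAR assessment in Section 15.3.4. As a pregnancy outcome, it has no stated deadline, and the protocol describes no step that turns it into an SAE report. Because the operative term is undefined, two sites could also classify the same conception after early discontinuation differently.

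**Working it through.** The plan gives no figure to reproduce. The check compares the reporting routes and then works out the timing in days.

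**Routes for a birth defect**

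| Route | Conception limit | Causality test | Deadline |
|---|---|---|---|
| Birth-defect rule (15.4.1) | Study treatment period | None | 24 hours, as an SAE |
| SAE up to the final Follow-Up Visit (15.3.2, 15.3.3) | None | None | 24 hours |
| SAE after that visit | None | Investigator considers it related | SAE reporting, only if that test is met |
| Pregnancy outcome (15.4.1, 15.6.1) | None | None | None stated for the outcome |

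**Inputs**

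- Final Follow-Up Visit: day 28 ± 5 after the last dose, so day 23 to 33 (Table 1).
- Conception: day 1 to 30 after the last dose (the avoidance window in 15.4.1).
- Conception to birth: about 266 days. This is an assumption, not in the documents; 154 to 280 days is used as a range to allow for earlier detection or delivery.

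**Step 1: when unconditional SAE reporting ends.** The window closes on day 30. Relative to the visit, 30 − 23 = 7 and 30 − 33 = −3. Unconditional reporting therefore stops between 7 days before and 3 days after the window closes.

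**Step 2: when the birth falls.** Day 1 + 266 = 267 to day 30 + 266 = 296 after the last dose.

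**Step 3: gap after the final visit.** Shortest: 267 − 33 = 234 days. Longest: 296 − 23 = 273 days. With the wider range, the shortest is 1 + 154 − 33 = 122 days and the longest is 30 + 280 − 23 = 287 days. On every assumption tested, the event comes after unconditional SAE reporting has ended.

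**Step 4: subjects who stay in the study after stopping treatment.** If the final visit is at Week 100 (day 700), a birth precedes it when the last dose is no later than 700 − 267 = day 433 (Week 61.9) for a day-1 conception, or 700 − 296 = day 404 (Week 57.7) for a day-30 conception. Those subjects remain inside the unconditional SAE window.

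**Step 5: the two meanings of the undefined term.** If it means actual dosing, every subject has the 30-day gap in the birth-defect rule. If it means the 96-week Treatment Period (672 days), a subject whose last dose is by day 672 − 30 = 642 (about Week 92) has no gap. A completer has the full 30 days on either reading.

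**Step 6: scale.** 200 subjects × 30 days = 6,000 days; 6,000 / 365.25 = 16.4 person-years. This counts everyone, whatever their childbearing potential, and contraception is required throughout.

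**The case against.** The strongest reply is that the sponsor would learn of the defect anyway. A birth defect is a pregnancy outcome. Sections 15.4.1 and 15.6.1 require pregnancies and their outcomes to be reported with no conception-date limit, end date or causality test. The general SAE definition has no conception limit either, and an event judged related stays reportable after the final visit. Section 15.3.4 lets the sponsor as well as the Investigator judge relatedness, so the Investigator is not the only gatekeeper once the sponsor has the information.

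Most of this stands. A reader might infer that birth defects from later conceptions are not reportable at all, or that the safety data are lost. The documents do not support that for a known pregnancy in a female subject. What the reply leaves open is the form and timing. The outcome has no stated deadline, and SAE entry after the final visit still depends first on the Investigator. The birth-defect sentence names offspring of male subjects, but the text does not say whether the pregnancy form covers their partners. The wording is not restricted to female subjects, and the Study Reference Guide, which was not available, may settle it.

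A second reply also stands in part. Section 10.1 lets subjects who discontinue treatment remain in the study, and those with a count below LLN continue visits. Early stoppers who do so can stay within unconditional SAE reporting (step 4). The gap therefore belongs mainly to subjects whose final visit is 4 weeks after the last dose, including those withdrawn for intolerance under Section 11.2.4.

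Finally, the protocol calls the 30 days a period of avoidance and contraception. It does not say that the fetus is exposed or at risk then; that is an inference from the requirement.

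**Conclusion.** The mismatch is real and lies within a single section. For subjects whose final Follow-Up Visit is 4 weeks after the last dose, a birth defect from a conception in the following 30 days would reach the sponsor only as a pregnancy outcome, or as an SAE if the Investigator judges it related. For early stoppers this assumes that *study treatment period* means actual dosing; for completers it holds on either reading. The timing rests on the assumed interval from conception to birth, but the conclusion is the same from 154 to 280 days.

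The size is a 30-day window per affected subject, with few events likely. A reader might size the harm as a share of days: 30/(672 + 30) = 4.3% for a completer, or 30/(84 + 30) = 26% after 12 weeks of treatment. These are proportions of calendar time. They do not measure missed reports, because the pregnancy-outcome duty still applies. The 12-week case is also a weak example: a conception on day 85 to 114 gives a birth near day 351 to 380, well before day 700 if the subject stays in the study. The case for changing the text rests on its inconsistency and the seriousness of each event, not on expected numbers.

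**What to change.** Reword the last sentence of Protocol 15.4.1 so that congenital abnormalities and birth defects are reported as SAEs, regardless of the Investigator's causality judgement, when conception occurred between the first dose and 30 days after the last dose. This matches the protocol's own window and removes the undefined term from the rule.

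Leave the duty to report pregnancies and outcomes without a conception window. Putting the 30-day limit on it could narrow a requirement that now has none. Add only that it includes pregnancies in partners of male subjects.

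The cost is one reworded sentence and one clarification in the next amendment, with a negligible number of extra SAE reports.
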